#### 4.3.5 *Underlying Disease History*

Count and percentage of recorded underlying disease history (recorded in the MH2 form of the eCRF) and associated classifications will be summarized by counts and percentages of subjects as appropriate by apaglutide dose levels and in total based on the FAS.

The primary classification of underlying diseases from MH2 form of the eCRF categories are as follows:

- Malignant – leukemia/ Myelodysplastic syndrome (MDS), which includes:
  - Acute myelogenous leukemia (AML or ANLL)
  - Acute lymphoblastic leukemia (ALL)
  - Acute leukemia of ambiguous lineage and other myeloid neoplasms
  - Chronic myelogenous leukemia (CML)
  - Myelodysplastic syndrome (MDS)
  - Myeloproliferative neoplasms (MPN)
  - Other leukemias
- Malignant – lymphoproliferative, which includes :
  - Hodgkin lymphoma
  - Non-Hodgkin lymphoma
  - Multiple myeloma / plasma cell disorder
- Non-malignant, which includes :
  - Aplastic anemia
  - Inherited bone marrow failure syndromes
  - Hemoglobinopathies
  - Paroxysmal nocturnal hemoglobinuria (PNH)
  - Disorders of immune system
  - Inherited abnormalities of platelets

- Inherited disorders of metabolism
- Histiocytic disorders
- Other, which includes :
  - Solid tumor
  - Other

In addition, time from diagnosis to first dose (days) will also be summarized using descriptive statistics for the FAS.

#### 4.3.6 *Treatment Duration and Compliance*

##### 4.3.6.1 *Apaglutide*

Treatment duration  $t$  for apaglutide will be calculated as the difference in days between the last treatment date  $d_l$ , increased by the planned dosed interval of 7 days, and the start treatment date  $d_s$ :  $t = (d_l + 7\text{days}) - d_s$ . Treatment duration for apaglutide will be calculated separately for i) the main treatment and the treatment extension, ii) the initial treatment (the main treatment, the treatment extension and the optional treatment) and iii) the flare treatment. Note that the treatment duration is intended to describe the length of time a subject was exposed to apaglutide and therefore does not take apaglutide interruptions into account. Treatment duration to apaglutide for the main treatment, the main treatment + treatment extension, the main treatment + treatment extension + optional treatment, and for the flare treatment will be summarized separately by apaglutide dose levels and in total on the SAS with descriptive statistics. Counts and percentages of subjects with exposure in the following categories will be summarized for the main treatment + treatment extension + optional treatment and for the flare treatment:

- $\leq 8$  weeks ( $\leq 56$  days)
- $> 8$  weeks and  $\leq 13$  weeks (57 to 91 days)
- $> 13$  weeks ( $\geq 91$  days) (not for the flare treatment).

Additionally, the number of apaglutide injections received per subject will also be summarized using descriptive statistics for the main treatment, the main treatment + treatment extension, the main treatment + treatment extension + optional treatment, and for the flare treatment respectively. The dose strength for apaglutide (computed as the ratio of actual cumulative dose received by treatment duration) will be summarized for the main treatment, the main treatment + treatment extension, the main treatment + treatment extension + optional treatment, and for the flare treatment.

Dose modifications will be summarized by type of modifications and reason of modification.

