## 2 TRIAL OVERVIEW

### 2.1 Trial Design

This is a randomized, single-blind, proof of concept (POC) trial to evaluate the safety, tolerability, and preliminary efficacy of apaglutide in subjects with Grade II to IV (MAGIC, Harris et al., 2016) Steroid Refractory (SR) gastrointestinal (GI) acute graft versus host disease (aGVHD) on systemic steroids (SS) and Ruxolitinib (RUX), defined as best available therapy (BAT). The overall trial design (Figure 1) is described below similarly to the trial synopsis from the protocol:

- Screening/Baseline:

The screening process can start any time after clinical diagnosis of lower GI-aGVHD and SS initiation. The subject should sign the Informed Consent Form (ICF) before any other trial procedure. This period will last at maximum 12 weeks (Days -84 to Day -1).

Subjects will be randomized (Day 0/Week 0) and receive the first dose of apaglutide only if they developed SR lower GI-aGVHD and have started treatment with RUX (at most 72 hours before starting apaglutide). Thirty subjects, weighing  $\geq 50.0$  kg, will be randomized to two treatment arms (high dose or low dose of apaglutide) based on their body weight at baseline (three body weight ranges:  $50.0 < 60.0$  kg,  $\leq 60.0 < 80.0$  kg and  $> 80.0$  kg). In addition to the 30 subjects, a separate, non-randomized cohort of up to four subjects with body weights within the range  $40.0 - < 50.0$  kg will be assigned to receive 2.5 mg of apaglutide.

- Main Treatment:

Up to 34 subjects will receive apaglutide on a background of RUX and SS. Apaglutide will be administered subcutaneously once weekly for 8 weeks (Week 0 to Week 7, inclusive).

- Treatment extension:

Treatment will continue up to 13 weeks (Week 8 to Week 12, inclusive) if no complete lower GI-aGVHD response is achieved at Week 8.

- Optional Treatment:

Optional treatment for additional 13 weeks (Week 13 to Week 25, inclusive) is allowed if no complete lower GI-aGVHD response is achieved at Week 13. Optional treatment can only be started if additional apaglutide treatment would benefit the subject based on the Investigator's judgement.

- Lower GI-aGVHD flare treatment:

Lower GI-aGVHD flare treatment can start if a subject develops a lower GI-aGVHD flare between Week 9 and Week 25. Only one event of lower GI-aGVHD flare can be treated with apraglutide until no later than Week 25.

- Follow-up:

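### In SAP 4.3.6.1 the apraglutide exposure categories overlap at exactly 91 days, the planned length of an on-schedule 13-dose course, because the more-than-13-weeks category is coded as 91 days or more

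*SAP*

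**What the plan says.** SAP 4.3.6.1 defines treatment duration as the difference between the last treatment date, "increased by the planned dosed interval of 7 days, and the start treatment date". No further day is added, and interruptions are ignored.

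The section then states: "Counts and percentages of subjects with exposure in the following categories will be summarized", once for main, extension and optional treatment together and once for flare treatment. The categories are:

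- up to 8 weeks, coded as 56 days or fewer;
- above 8 and up to 13 weeks, coded as "weeks (57 to 91 days");
- more than 13 weeks, coded as 91 days or more, with the rider "days) (not for the flare treatment").

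The dosing schedule is in SAP 2.1. Main treatment is "administered subcutaneously once weekly for 8 weeks (Week 0 to Week 7, inclusive"). For subjects without a complete lower GI response at Week 8, "Treatment will continue up to 13 weeks (Week 8 to Week 12, inclusive"). Optional treatment after that requires no complete response at Week 13 and the investigator's judgement that the subject would benefit.

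SAP 4.3.6.1 has no rule for a duration of exactly 91 days, and SAP Section 6 does not mention the point.

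**The concern.** The middle and top day ranges share one value, 91 days, and that value is the planned duration of the full 13-dose course. The group that can land on it is foreseen by the design. Table B1, footnote 3, in SAP Appendix B keeps subjects without a Week 8 complete response on treatment through Week 12. Protocol 2.2.2 expressly contemplates treatment having stopped with a partial or complete response at Day 91.

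If the day ranges are programmed as printed, those subjects may appear in two rows of the table, or in the top row without ever having entered optional treatment. Safety is the primary objective (Protocol 1.5.1.1), and earlier repeated dosing is described as up to six weekly doses (Protocol 1.4). A reader will therefore use this table to see how many subjects were exposed for longer than 13 weeks.

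**Working it through.** **Inputs.** Duration formula and category ranges: SAP 4.3.6.1. Weekly schedule: SAP 2.1. Visit window of ±1 day: SAP Appendix B, Table B1. Planned numbers: 15 per dose arm and up to 34 in total (Protocol 7.4 and synopsis).

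**Formula.** t = (last dose date + 7) − first dose date. With the first dose on Day 0 and the last at Week w, t = 7w + 7.

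**The plan's cut-points.** 8 × 7 = 56 and 13 × 7 = 91, so the upper limits of the first two categories reproduce. The lower limit of the top category does not: more than 13 weeks means more than 91 days, which in whole days is 92 or more.

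**Planned courses.**

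| Last dose | t (days) | Day ranges met as printed | Category by week label |
|---|---|---|---|
| Week 7, on schedule | 49 + 7 = 56 | first only | up to 8 weeks |
| Week 7, one day late | 50 + 7 = 57 | middle only | above 8, up to 13 weeks |
| Week 12, one day early | 83 + 7 = 90 | middle only | above 8, up to 13 weeks |
| **Week 12, on schedule** | **84 + 7 = 91** | **middle and top** | **above 8, up to 13 weeks** |
| Week 12, one day late | 85 + 7 = 92 | top only | more than 13 weeks |
| Week 25, on schedule | 175 + 7 = 182 | top only | more than 13 weeks |

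**All durations.** Classifying every whole-day duration from 1 to 189 by the printed day ranges, 91 is the only one that does not fall in exactly one category. By the week labels, every duration falls in exactly one. With the top range set to 92 days or more, the day ranges are also exclusive and exhaustive.

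**What happens to the table.** Let k be the number of subjects with t = 91 and N the denominator. The result depends on how the conditions are coded:

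- separate flags: the percentages sum to 100% + 100k/N;
- top condition takes precedence: the top row is too high by k and the middle row too low by k;
- middle condition takes precedence: the table is correct.

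The documents do not give k. It can be anything from 0 upwards, so only the size per affected subject can be stated: 1/34 = 2.9 percentage points in a total column of 34, or 1/15 = 6.7 points in a dose arm of 15. Both assume the planned numbers are reached.

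**The case against.** The strongest reply is that the week labels already settle the matter. They are mutually exclusive, 91 days is exactly 13.0 weeks, and it belongs in the middle category. On that reading the fault is one sign in a parenthesis, and a programmer working from the labels would get the table right. SAP Section 5 places the programming specifications in a separate document, so double-counting is possible but not shown. A sign altered in converting the SAP to text cannot be ruled out either. All of this stands as a limit on the consequence. It does not remove the contradiction between the top category's label and its day range, and the SAP does not say which governs.

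It is also fair to say that the table is descriptive. SAP 4.3.6.1 separately summarises duration and number of injections, with and without optional treatment, so a miscount could be noticed.

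Three stronger readings are tempting, and the documents do not support them.

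- *The ±1 day window creates the same error at both cut-offs.* It does not. The SAP measures calendar duration. 57 days is more than 8 weeks and 92 days is more than 13 weeks, so each is classified once and correctly.
- *The more-than-13-weeks row will be inflated by a substantial, known amount.* The number affected depends on how many subjects had no complete response at Week 8, a last dose exactly on Day 84, and no optional treatment. None of these counts is given.
- *The categories should be rebuilt on injection counts.* Missed doses are not made up (Protocol 6.6.2). A subject treated from Week 0 to Week 12 with five doses held would have 91 days of exposure but 13 − 5 = 8 injections, and would drop into the lowest category. That changes what is measured.

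**Conclusion.** The day ranges are wrong as written. A duration of 91 days meets two categories, and 91 days or more is not the day equivalent of more than 13 weeks. Because 91 days is the planned length of an on-schedule 13-dose course, the overlap falls on a foreseeable group and not on a rare value.

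The reach is small. It affects only the categorical exposure summary for main, extension and optional treatment. The flare summary does not use the top category, and no efficacy, adverse-event or sample-size result changes. Whether any output is actually wrong depends on the coding and on the number of subjects at exactly 91 days, neither of which the documents show. The arithmetic rests only on the SAP's own formula and schedule.

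**What to change.** Change the top day range to 92 days or more (equivalently, more than 91 days) in SAP 4.3.6.1 and in the programming specifications. Confirm that any Primary Analysis output already produced used mutually exclusive categories, and rerun that table if it did not. Keep the categories based on duration, since injection counts are already summarised separately in the same section. The cost is one corrected number and a check of one table, with no new data.

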#### 4.3.6.2 *Systemic Steroids (SS) and Ruxolitinib (RUX)*

The weekly weight-normalized cumulative RUX dose strength (mg/kg), and the weekly weight-normalized cumulative SS dose strength (mg/kg) will be summarized using descriptive statistics by apaglutide dose levels and in total on the SAS, for each week from Visit Day 0 to Visit Day 91. In case weekly records are not available for a given week, doses will be imputed as follows:

- 0 mg/kg if patient was tapered off
- The largest value between the closest records collected prior to and after the given week.

Imputation will be performed until Day 91, trial discontinuation or death, whichever occurs first.

The weight at baseline will be used to derive the normalization. Boxplots colored by treatment group (only displaying Low Dose and High Dose) will be produced for the average weekly weight-normalized Ruxolitinib and Systemic Steroids dosing.

The converted systemic Methylprednisolone equivalent dose in mg will be used for the systemic steroids summaries. Systemic Methylprednisolone equivalent dose conversions in mg for 1 mg of Methylprednisolone are presented in Table 4-1: Systemic Methylprednisolone equivalent dose conversion. For instance, 5mg of Hydrocortisone will be converted to an equivalent dose of 1 mg of Methylprednisolone, using a Methylprednisolone equivalent conversion factor for Hydrocortisone equal to 0.2.

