4.2.2 Ruxolitinib and Steroid Medications

4.2.2.1 Ruxolitinib Dose Adjustments

Dose reductions and temporary interruptions of RUX treatment may be needed in SR lower GI-aGVHD subjects with thrombocytopenia, neutropenia, or elevated total bilirubin after standard supportive therapy, including growth-factors, anti-infective therapies, and transfusions. Dose adjustment recommendations for RUX should be followed according to the current regional recommendations (the European Union Prescribing Information [EUPI] and United States Prescribing Information [USPI]).

Dose adjustments of RUX should be documented in the source documentation and in the relevant eCRF page.

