- Cumulative SS and RUX doses from start of the RUX treatment up to Day 91 after the first dose of apaglutide [Only for Primary Analysis]
- Incidence of infections and sepsis from baseline to Day 91 and overall after the first dose of apaglutide

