  - ICE6: Budesonide use or other non-absorbable steroids given orally: following treatment policy, observed values will be used regardless of the ICE.
  - ICE10 (additional from interim analysis): interruption of 14 or more days of RUX, as per “treatment policy” strategy, all observed values will be used regardless of the ICE.
- Other:
  - ICE7: Underlying hematological disease progression or relapse, following treatment policy, all observed values will be used regardless of the ICE.
  - ICE8: Development of cGVHD, following treatment policy, all observed values will be used regardless of the ICE.
  - ICE9: CTR-reportable protocol deviation that significantly affects subject safety or efficacy (as defined in the Protocol Deviation Plan), all observed values will be used regardless of the ICE.

The number and percentage of subjects with overall response (PR and CR) at Day 56 on the Lower GI MAGIC score along with the two-sided 95% confidence intervals using Clopper-Pearson exact method will be provided by apraglutide dose levels and in total. In addition, the number and percentage of subjects with CR and the number and percentage of subjects with PR at Day 56 on the Lower GI MAGIC score will also be summarized, respectively.

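### The SAP's imputation rule for steroid and ruxolitinib doses has no branch for a temporary hold, and the listed cumulative-dose endpoint has no clearly specified per-subject analysis

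*SAP*

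**What the plan says.** SAP 4.3.6.2 plans descriptive summaries of a weekly, weight-normalised cumulative dose of SS and of RUX, "for each week from Visit Day 0 to Visit Day 91", with boxplots of average weekly dosing. It then states: "In case weekly records are not available for a given week, doses will be imputed as follows". Two outcomes follow. The first is "0 mg/kg if patient was tapered off". The second, for every other such week, is "The largest value between the closest records collected prior to and after the given week". The end point of the rule is also stated: "Imputation will be performed until Day 91, trial discontinuation or death, whichever occurs first". This replaces the general position in SAP 4.1.2, where only observed values enter descriptive statistics unless otherwise specified.

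Protocol 4.2.2.1 says "Dose reductions and temporary interruptions of RUX treatment may be needed in SR lower GI-aGVHD subjects", and gives thrombocytopenia, neutropenia and raised bilirubin as the reasons. That section and Protocol 4.2.3.2 require SS and RUX doses and their adjustments to be entered in the eCRF. SAP 4.3.9.2 lists "interruption of 14 or more days of RUX" as ICE10.

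The secondary endpoint in SAP 3.2 is "Cumulative SS and RUX doses from start of the RUX treatment up to Day 91 after the first dose" of apraglutide. It is marked for the Primary Analysis only, and Protocol 1.5.2.2 lists the same endpoint. Under inclusion criterion 7, RUX may start together with apraglutide or up to 72 hours before it.

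**The concern.** A hold is not a taper, a trial discontinuation or a death. A held week that leaves no record therefore falls through to the second outcome and receives the larger neighbouring dose. The same subject could then be an ICE10 case, counted as a non-responder in the Day 56 sensitivity analysis, and also be shown as dosed throughout in the exposure table.

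The exposure table carries weight in this trial. Section 6 item 7 of the SAP drops the comparison with external data for the Primary Analysis. SAP Appendix A does not count a steroid increase, or an added systemic steroid, as new GVHD therapy, so a subject can be a responder after escalation. Background SS and RUX exposure is then a main way to see whether response came with more or less immunosuppression. It also shows how well RUX was tolerated, in a trial whose primary objective is safety on this background.

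The second issue is the endpoint. The quantity listed in SAP 3.2 is one cumulative dose per subject over a window that opens at RUX start. The only related analysis text is organised by week and opens at Visit Day 0.

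**Working it through.** The plan gives no figure to reproduce here. The check applies the written rule to a simple dosing history and then compares the endpoint with its analysis text.

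**Inputs**
- Window: Visit Day 0 to Visit Day 91 (SAP 4.3.6.2), so 91 / 7 = 13 weeks.
- Rule: maximum of the nearest earlier and nearest later record (SAP 4.3.6.2).
- RUX lead time: 0 to 72 hours, i.e. 0 to 3 days (Protocol 3.2.1, criterion 7).
- Assumptions, because the documents give no RUX dose and no hold frequency: full dose = 1 unit per week; a hold of h whole weeks, h = 1 to 4; the hold leaves no weekly record.

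**Full dose resumed after the hold**

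Dose taken = 13 − h. Dose under the rule = 13. Overstatement = 13 / (13 − h) − 1.

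| Hold (weeks) | Taken | Under the rule | Overstatement |
|---|---|---|---|
| 1 | 12 | 13 | 8.3% |
| 2 (ICE10 threshold) | 11 | 13 | 18.2% |
| 3 | 10 | 13 | 30.0% |
| 4 | 9 | 13 | 44.4% |

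**Half dose resumed, hold starting after week 5**

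Dose taken = 5 + 0.5 × (8 − h). The rule adds h units, because the pre-hold dose is the larger neighbour.

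| Hold (weeks) | Taken | Under the rule | Overstatement |
|---|---|---|---|
| 1 | 8.5 | 9.5 | 11.8% |
| 2 | 8.0 | 10.0 | 25.0% |
| 3 | 7.5 | 10.5 | 40.0% |
| 4 | 7.0 | 11.0 | 57.1% |

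These are effects on one subject's 13-week total. In a weekly summary the effect is confined to the held weeks. With 15 subjects in an arm, 14 on full dose and one on hold, that week's true mean is 14/15 = 0.93 units and the rule gives 1.00, which is 15/14 − 1 = 7.1% too high.

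**Share of the endpoint window that is omitted**

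At constant dose, with RUX started d days before Day 0, the omitted share is d / (91 + d): 0% for d = 0, 1.1% for 1 day, 2.2% for 2 days and 3.2% for 3 days.

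**Endpoint against analysis text**
- None of SAP 4.3.9.1 to 4.3.9.17 analyses cumulative SS or RUX dose.
- The variable in 4.3.6.2 is called both weekly and cumulative. As a total within each week, it gives no total per subject.
- As a running total with the imputation applied to it directly, the zero for a tapered subject would reset the total, and the larger neighbour would always be the later week. The rules do not fit that reading.
- As a running total built after weekly doses are imputed, the last week would be a per-subject total, but one counted from Visit Day 0.
- On none of these readings does the window open at RUX start. Section 6 lists other endpoint changes, including a removed endpoint (item 12), but not this one.

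**The case against.** The strongest reply is that a documented hold is not missing data. The protocol requires RUX adjustments and exact doses in the eCRF, the imputation applies only where records are unavailable, and ICE10 can be derived only if interruptions are recorded. A hold entered as 0 mg would never be imputed. This stands as a limit. A reader might infer that RUX exposure will be overstated as the SAP is written; the documents support only that it can be, depending on how holds are represented, which the SAP does not say. That interruptions must be identifiable for ICE10 also shows that the fix is feasible.

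A second reply is that the larger neighbour is a cautious choice against any claim of dose sparing. That is fair where the drug was ongoing and the dose unknown. It is not fair for a hold, where it can hide RUX intolerance.

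Third, the word cumulative in 4.3.6.2 may be meant as a running total, and SAP Section 5 places output specifications in a separate document. A reader might therefore go too far in concluding that no per-subject total will be produced. What can be said is that the SAP does not clearly specify one.

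Fourth, the consequences are bounded. The summaries are descriptive, with no formal dose-group comparison, and ICE10 has its own sensitivity analysis for Day 56 response. RUX given before Day 0 is reserved for exceptional cases. Stopping imputation at death or discontinuation is normal practice, so later weeks describing only subjects still on study is not an error.

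**Conclusion.** The concern holds in a conditional form. The imputation rule lacks a branch for temporary interruption. If holds appear as gaps, one subject's 13-week total would be overstated by 8% to 44% for holds of 1 to 4 weeks with full dose resumed, and by 12% to 57% with half dose resumed. These figures rest on a constant dose before the hold, whole-week holds and no record during the hold. The number of subjects affected cannot be estimated from the documents.

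The endpoint gap does not depend on how holds are coded. A listed secondary endpoint, due at the Primary Analysis only, has no clearly specified per-subject analysis, and its window is moved without declaration. The moved window costs at most about 3% of the dose and is minor; the unclear per-subject total is the larger part of this issue.

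**What to change.** In SAP 4.3.6.2:

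1. State how a hold is represented in the dosing data. Set every week that lies within a documented interruption to 0, prorated if the interruption covers only part of the week.
2. Restrict the larger-neighbour rule to weeks in which the drug was ongoing and the dose is unknown. Show an observed-records-only summary beside it.
3. Add the per-subject cumulative SS dose (methylprednisolone-equivalent mg/kg) and RUX dose (mg/kg) from RUX start to Day 91, summarised by dose group, and state how death and discontinuation are handled. If this is not wanted, declare the change of endpoint in Section 6.

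A version per day alive and on study would help keep early death from looking like dose sparing. It is an optional supplement.

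The cost is a few lines of SAP text and one derived variable per drug, from dosing data that the protocol already requires. No new data are needed and no clinical rule changes.
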